5.4.3 Reporting Requirements for Pregnancies

5.4.3.1 Pregnancies in Female Patients

Female patients of childbearing potential will be instructed *through the Informed Consent Form* to immediately inform the investigator if they become pregnant during the study or within 90 days after the final dose of RO7198457 or 4 months after the final dose of pembrolizumab, whichever occurs later. A paper Clinical Trial Pregnancy Reporting Form should be completed and submitted to the Sponsor or its designee immediately (i.e., no more than 24 hours after learning of the pregnancy), either by faxing or by scanning and emailing the form using the fax number or email address provided to investigators. Pregnancy should not be recorded on the Adverse Event eCRF. The investigator should discontinue study drug and counsel the patient, discussing the risks of the pregnancy and the possible effects on the fetus. Monitoring of the patient should continue until conclusion of the pregnancy. Any serious adverse events associated with the pregnancy (e.g., an event in the fetus, an event in the mother during or after the pregnancy, or a congenital anomaly/birth defect in the child) should be reported on the Adverse Event eCRF. In addition, the investigator will submit a Clinical Trial Pregnancy Reporting Form when updated information on the course and outcome of the pregnancy becomes available.

5.4.3.2 Pregnancies in Female Partners of Male Patients

Male patients will be instructed through the Informed Consent Form to immediately inform the investigator if their partner becomes pregnant during the study or within 28 days after the final dose of study treatment. *The investigator should report the pregnancy on the paper Clinical Trial Pregnancy Reporting Form and submit the form to the Sponsor or its designee immediately (i.e., no more than 24 hours after learning of the pregnancy), either by faxing or by scanning and emailing the form using the fax number or email address provided to investigators. Attempts should be made to collect and report details of the course and outcome of any pregnancy in the partner of a male patient exposed to study drug. When permitted by the site, the pregnant partner would need to sign an Authorization for Use and Disclosure of Pregnancy Health Information to allow for follow-up on her pregnancy. If the authorization has been signed, the investigator should submit a Clinical Trial Pregnancy Reporting Form with additional information on the pregnant partner and the course and outcome of the pregnancy as it becomes available. An investigator who is contacted by the male patient or his pregnant partner may provide information on the risks of the pregnancy and the possible effects on the fetus, to support an informed decision in cooperation with the treating physician and/or obstetrician.*

5.4.3.3 Abortions

A spontaneous abortion should be classified as a serious adverse event (as the Sponsor considers abortions to be medically significant), recorded on the Adverse Event eCRF, and reported to the Sponsor immediately (i.e., no more than 24 hours after learning of the event; see Section [5.4.2](#)).

If a therapeutic or elective abortion was performed because of an underlying maternal or embryofetal toxicity, the toxicity should be classified as a serious adverse event, recorded on the Adverse Event eCRF, and reported to the Sponsor immediately (i.e., no more than 24 hours after learning of the event; see Section [5.4.2](#)). A therapeutic or elective abortion performed for reasons other than an underlying maternal or embryofetal toxicity is not considered an adverse event.

All abortions should be reported as pregnancy outcomes on the paper Clinical Trial Pregnancy Reporting Form.

5.4.3.4 Congenital Anomalies/Birth Defects

Any congenital anomaly/birth defect in a child born to a female patient exposed to study drug or the female partner of a male patient exposed to study drug should be classified as a serious adverse event, recorded on the Adverse Event eCRF, and reported to the Sponsor immediately (i.e., no more than 24 hours after learning of the event; see Section [5.4.2](#)).

5.5 FOLLOW-UP OF PATIENTS AFTER ADVERSE EVENTS

5.5.1 Investigator Follow-Up

The investigator should follow each adverse event until the event has resolved to baseline grade or better, the event is assessed as stable by the investigator, the patient is lost to follow-up, or the patient withdraws consent. Every effort should be made to follow all serious adverse events considered to be related to study drug or trial-related procedures until a final outcome can be reported.

During the study period, resolution of adverse events (with dates) should be documented on the Adverse Event eCRF and in the patient's medical record to facilitate source data verification.

All pregnancies reported during the study should be followed until pregnancy outcome.

5.5.2 Sponsor Follow-Up

For serious adverse events, adverse events of special interest, and pregnancies, the Sponsor or a designee may follow up by telephone, fax, email, and/or a monitoring visit to obtain additional case details and outcome information (e.g., from hospital discharge summaries, consultant reports, autopsy reports) in order to perform an independent medical assessment of the reported case.

5.6 ADVERSE EVENTS THAT OCCUR AFTER THE ADVERSE EVENT REPORTING PERIOD

After the end of the adverse event reporting period (defined as 90 days after the final dose of study drug), all deaths, regardless of cause, should be reported through use of the Long-Term Survival Follow-Up eCRF.

In addition, if the investigator becomes aware of a serious adverse event that is believed to be related to prior exposure to study drug, the event should be reported through use of the Adverse Event eCRF. However, if the EDC system is not available, the investigator should report these events directly to the Sponsor or its designee, either by faxing or by scanning and emailing the paper Clinical Trial Serious Adverse Event/Adverse Event of Special Interest Reporting Form using the fax number or email address provided to investigators.

5.7 EXPEDITED REPORTING TO HEALTH AUTHORITIES, INVESTIGATORS, INSTITUTIONAL REVIEW BOARDS, AND ETHICS COMMITTEES

The Sponsor will promptly evaluate all serious adverse events and adverse events of special interest against cumulative product experience to identify and expeditiously communicate possible new safety findings to investigators, IRBs, ECs, and applicable health authorities based on applicable legislation.

To determine reporting requirements for single adverse event cases, the Sponsor will assess the expectedness of these events using the following reference documents:

- RO7198457 Investigator's Brochure
- Pembrolizumab Summary of Product Characteristics (SmPC)

The Sponsor will compare the severity of each event and the cumulative event frequency reported for the study with the severity and frequency reported in the applicable reference document.

Reporting requirements will also be based on the investigator's assessment of causality and seriousness, with allowance for upgrading by the Sponsor as needed.

6. STATISTICAL CONSIDERATIONS AND ANALYSIS PLAN

This study will include an initial safety run-in stage followed by a randomization stage. During the safety run-in stage, 6–12 patients with metastatic melanoma will be enrolled and treated with RO7198457 and pembrolizumab. Following IMC review, enrollment will be opened for the randomization stage.

The randomization stage will enroll approximately 120 patients that will represent the ITT population for the primary PFS and secondary activity endpoints. Unless otherwise stated, summaries of study conduct, patient demographics, baseline characteristics, and secondary and exploratory endpoints will be assessed in all randomized patients and separately for patients in the safety run-in stage.

6.1 DETERMINATION OF SAMPLE SIZE

The purpose of this study is estimation and hypothesis generation regarding the safety and efficacy of RO7198457 plus pembrolizumab relative to pembrolizumab monotherapy.

Enrollment of 120 randomized patients (approximately 80 patients in the RO7198457 plus pembrolizumab arm and 40 patients in the standard-of-care arm) is expected to occur 18 months after first patient in (FPI).

The null and alternative hypotheses with respect to PFS can be phrased in terms of the survival function $S_{PFS_a}(t)$ in Arm A (control) and $S_{PFS_b}(t)$ in Arm B (experimental):

$$H_0: S_{PFS_a}(t) = S_{PFS_b}(t) \text{ vs. } H_a: S_{PFS_a}(t) \neq S_{PFS_b}(t)$$

in our PFS primary efficacy endpoint, the first efficacy endpoint tested in a hierarchical fashion. However, the totality of data, including safety and sensitivity analyses while accounting for non-proportional hazards as stated in Section 6.4.1 will be important for evaluating clinical benefit.

Point and interval estimates for the primary endpoint of PFS HR and key secondary endpoint of improvement in ORR (i.e., Δ ORR) in the RO7198457 plus pembrolizumab arm relative to the pembrolizumab arm will be obtained.

To control for Type 1 error, two pre-specified interim analyses and one primary analysis will be conducted with a Haybittle-Peto alpha spending approach (Haybittle 1971; Peto et al. 1976). Testing will be performed in a hierarchical fashion testing PFS followed by secondary endpoints. Each interim analysis will be conducted at the two-sided significance level of 0.001. The final analysis will be conducted at the two-sided significance level of 5%. If PFS is significant at the two-sided significance level of 5%, alpha will be passed down to the secondary endpoints in order of presentation below.

The study will not, however, have adequate power to detect other potentially clinically meaningful differences in PFS and Δ ORR.

improvement in ORR in the RO7198457 plus pembrolizumab arm relative to the pembrolizumab arm (assuming a 33% ORR in the pembrolizumab arm). Thus, a statistically negative outcome does not rule out a potentially clinically meaningful outcome.

[Table 11](#) and [Table 12](#) show the power and CIs for several possible true underlying improvements in PFS and ORR in favor of the RO7198457 plus pembrolizumab arm. The study will not have adequate power to detect other potentially clinically meaningful differences in PFS or ORR. See [Table 11](#) below.

Table 11 Power and Confidence Intervals for Study Design for Several Possible True Underlying PFS Hazard Ratio Values

True Underlying PFS Hazard Ratio
[REDACTED]

PFS=progression-free survival.

Notes: Results are based on 80 total events from 120 total patients in a 2:1 ratio

^a Two-sided $\alpha=0.05$

Table 12 Power and Confidence Intervals for Study Design for Several Possible True Underlying Δ ORR Values

True Underlying Δ ORR

ORR=objective response rate.

Notes: Results are based on 120 total patients (80 and 40 patients in the treatment and control arm, respectively).

^a Two-sided $\alpha=0.05$

6.2 SUMMARIES OF CONDUCT OF STUDY

Enrollment, study treatment administration, and discontinuation from the study will be summarized by treatment arm. The reasons for study treatment discontinuation will also be tabulated. Major protocol deviations, including major deviations with regard to the inclusion and exclusion criteria, will be listed by treatment arm and evaluated for their potential effects on the interpretation of study results.

6.3 SUMMARIES OF DEMOGRAPHIC AND BASELINE CHARACTERISTICS

Demographic and baseline characteristics such as age, sex, race, weight, stage, and baseline ECOG Performance Status will be summarized by treatment arm for all randomized patients. Descriptive summaries of continuous data will present the group mean, standard deviation, median, minimum, and maximum. Descriptive summaries of discrete data will present the category counts as frequencies and percentages.

6.4 EFFICACY ANALYSES

The primary analysis population includes all patients randomized (i.e., the intent-to-treat [ITT] population). Supportive per protocol analysis populations will include patients on-study at Cycle 2 receiving intended treatment (e.g., patients who received at least 2 cycles of study treatment) as well as safety run-in stage patients. The primary analysis will be PFS.

6.4.1 Primary Efficacy Endpoint of PFS

PFS is defined as the time from randomization to the date of first documented disease progression or death, whichever occurs first. Disease progression for PFS analysis will be determined on the basis of investigator assessment using RECIST v1.1. The primary PFS analysis will occur after approximately 80 events have been observed in the primary population or approximately 24 months from FPI.

Data for a patient without disease progression or death as of the clinical data cutoff date will be censored at the time of the last tumor assessment (or at the date of randomization plus 1 day if no tumor assessment was performed after the baseline visit). Data from a patient who is lost to follow-up will be included in the analysis and censored on the last date of tumor assessment that the patient was known to be progression free.

Kaplan-Meier methodology will be used to estimate the PFS curve and median PFS for each treatment arm. A stratified Cox proportional-hazards model will be used to estimate the HR and its 95% CI. The two-sided stratified log-rank test will be used to compare PFS between the two treatment arms at the two-sided significance level of 5%. Unstratified modeling approaches may be used to assess the robustness of the PFS primary endpoint results. To account for patients who may discontinue study treatment prior to first administration of RO7198457, a landmark analysis restricted to patients treated at Cycle 2 and beyond may be performed with PFS time calculated starting from Cycle 2, Day 1 on the ITT and modified subsets.

6.4.2 Secondary Efficacy Endpoints

ORR Analysis

ORR is defined as the proportion of patients who have experienced a CR or PR on two consecutive occasions \geq 4 weeks apart, as determined by the investigator according to RECIST v1.1. Objective response will be evaluated by treatment arm. Patients without postbaseline overall response assessments will be counted as non-responders. An estimate of the difference between the ORR in the two arms will be computed along with its 95% CI. The Mantel-Haenszel test will be used to compare the ORR between the two treatment arms at the two-sided significance level of 5%, if PFS analysis is significant at the 5% threshold for type I error control, stratified by the protocol-defined stratification factors. Final ORR analysis will occur at the time of primary PFS analysis.

OS Analysis

OS is defined as the time from randomization to death from any cause. Data for patients who are alive at the time of the analysis data cutoff will be censored at the last date they were known to be alive. Data from patients without postbaseline information will be censored at the date of randomization plus 1 day. A final OS analysis will be performed at approximately 40% event maturity at approximately 40 months. Statistical analyses will be performed similarly to PFS as described in [6.4.1](#).

Duration of Response Analysis

DOR is defined as the time from the first occurrence of a documented objective response to disease progression or death from any cause, whichever occurs first, as determined by the investigator according to RECIST v1.1. The analysis of DOR will include only patients who achieved an objective response to study treatment. DOR will be estimated using the Kaplan-Meier methodology.

Crossover Analysis

The statistical analysis to evaluate the efficacy of patients who have progressed following pembrolizumab monotherapy and received the combination of RO7198457 plus pembrolizumab as assessed by ORR per RECIST v1.1 will be performed as described in Section 6.4.2.

Patient-Reported Outcomes Analysis

Summary statistics and longitudinal analyses will inform change from baseline in GHS/HRQoL scores at each timepoint (including baseline, end of induction, crossover for Arm A, time to first PD per RECIST v1.1, end of treatment for any cause) by treatment arm during treatment will be analyzed for all randomized patients who had a baseline and one or more postbaseline assessments. A score change of at least 10 points is considered clinically meaningful and will be used to define deterioration and improvement.

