3.1.5 Internal Monitoring Committee Reviews

The primary responsibility of the IMC is to review the available safety data and make recommendations on study conduct to ensure enhanced patient safety while patients receive study treatment. The IMC will periodically evaluate the accumulating safety data from all patients treated in this study. Following analysis of the primary endpoint of PFS, expected to occur approximately 24 months after enrollment of the first randomized patient, future safety analyses will be conducted. The IMC Chair will be a medical oncologist who is not the Medical Monitor and is not associated with the study. Other IMC members may include, but are not limited to, a safety scientist, biostatistician, and clinical pharmacologist. The IMC will operate according to a pre-specified charter and make recommendations on study conduct related to patient safety (see Section 5).

The IMC will review the safety data during the safety run-in stage as described in Section 3.1.2. During the randomization stage, safety data from the first 20 patients in Arm B treated with at least 1 cycle of RO7198457 plus pembrolizumab will be formally reviewed by an IMC. Following the initial data reviews in the safety run-in and randomization stages, the IMC will review the safety data approximately every 6 months, or more frequently if recommended by the IMC Chair or the Medical Monitor. The safety data may include, but are not limited to, demographic data, adverse event data (including serious adverse events and adverse events of special interest), study conduct data, and relevant laboratory data.

In addition, the Medical Monitor may request additional safety reports and may call for ad-hoc meetings of the IMC at any time during the study to review ongoing safety data for a benefit-risk balance.

The IMC may make recommendations regarding study conduct, including, but not limited to, the following: continuing the study as per the protocol, performing additional safety analyses, amending the study protocol, holding patient enrollment pending further safety evaluations, holding/discontinuing study treatment, or terminating the study.

The IMC may share preliminary results from these safety and interim analyses with appropriate Sponsor employees and with the investigators, as the IMC Chair deems necessary.

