Results of standard of care tests or examinations performed prior to obtaining Informed Consent and ≤ 28 days prior to *Day 1 of Cycle 1* may be used for the purposes of screening rather than repeating such tests. All measurable and evaluable lesions should be re-assessed at each subsequent tumor evaluation. The same radiographic procedures used to assess disease sites at screening should be used throughout the study (e.g., the same contrast protocol for CT scans).

Response will be assessed on the basis of the Investigator's physical examinations and the imaging modalities detailed above, using both RECIST v1.1 and iRECIST criteria (see [Appendix 4](#) and [Appendix 5](#), respectively). The investigator's assessment of overall tumor response at all timepoints should only be based on RECIST v1.1. Assessments should be performed by the same evaluator if possible to ensure internal consistency across visits. Results must be reviewed by the investigator before dosing the next cycle.

The timing of tumor assessments will be determined based on weeks from first study treatment (C1D1; pembrolizumab monotherapy) and will not be tied to cycle-specific visits. The purpose of having the tumor assessments independent of cycle-specific visits is so that they occur at the same interval for all patients, regardless of delays in dosing.

Tumor assessments must be obtained and documented during Screening Part B (to establish a baseline assessment prior to Cycle 1, Day 1), during Week 12, and then every 6 weeks thereafter for the first 48 weeks (i.e., during Weeks 12, 18, 24, 30, 36, 42, and 48). *"During week" is defined as the first day/Day 1 of each targeted week (e.g., 12, 18, or 24 weeks from C1D1 date) plus 6 calendar days.* After Week 48, tumor assessments will occur every 12 (± 1) weeks through Week 96 (i.e., during Weeks 60, 72, 84, and 96). After Week 96, follow-up tumor assessments will occur approximately every 12 weeks through Week 156 (i.e., Weeks 108, 120, 132, 144, and 156). After Week 156, follow-up tumor assessments will occur approximately every 24 weeks (i.e., Weeks 180, 204, 228, and 252); see also [Appendix 1](#) and [Appendix 2](#).

Per investigator discretion, tumor assessments may also occur as clinically indicated.

If applicable, cutaneous lesions are to be obtained by digital photography and documented at each tumor assessment as described in Section [4.5.6](#).

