6.8 INTERIM ANALYSES

6.8.1 Planned Interim Analyses

Periodic analyses of cumulative safety data and two interim analyses of efficacy data are planned for this study. Safety interim analyses will be conducted at regular intervals by the IMC (see [Section 3.1.5](#)).

The first efficacy interim analysis will take place after either approximately 60 patients have had two scans or 25% PFS event maturity, both of which are expected to occur at approximately 16 months after FPI. The second interim analysis will occur at approximately 50% event maturity, which is expected to be around 18 months.

Outcomes from these reviews that may affect study conduct will be communicated in a timely manner to the investigators, and IRBs and/or ECs will be notified. Any changes to the study design resulting from these analyses will be addressed through a protocol amendment.

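### Final confirmed ORR is cut with the PFS analysis and has no follow-up floor, so an early 80-event cut or slow accrual would count patients as non-responders before a confirming scan was possible

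*Combined protocol and SAP*

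**What the plan says.** Section 6.4.2 counts a response only when CR or PR is seen at two consecutive assessments four or more weeks apart. On timing it says: "Final ORR analysis will occur at the time of primary PFS analysis". On patients with no data it says: "Patients without postbaseline overall response assessments will be counted as non-responders". Sections 6 and 6.4 keep all randomised patients as the analysis population.

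Section 4.5.5 schedules tumour assessments at baseline, then "during Week 12, and then every 6 weeks thereafter for the first 48 weeks". Weeks run from Cycle 1 Day 1, and each visit has a window of six further days. Section 4.2 asks for the first dose within about a week of randomisation.

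The cut itself is set in Section 6.4.1: "The primary PFS analysis will occur after approximately 80 events have been observed in the primary population or approximately 24 months from FPI". The text does not say whether the earlier or the later of the two applies. Section 3.1.5 describes the same analysis as "expected to occur approximately 24 months after enrollment of the first randomized patient". Section 6.1 expects all 120 patients ("approximately 80 patients in the RO7198457 plus pembrolizumab arm and 40 patients in the standard-of-care arm") to be enrolled 18 months after FPI.

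**The concern.** The final ORR inherits a cutoff chosen for PFS. PFS tolerates short follow-up because Section 6.4.1 censors a patient without an event at the last assessment. ORR does not. A patient with no post-baseline scan is a non-responder by rule, and a patient with a response at Week 12 and no second scan yet fails the confirmation requirement. Neither rule separates patients who did not respond from patients who could not yet have a confirmed response.

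The ORR difference is the key secondary endpoint and follows PFS in the testing order. Section 6.1 also says that its point and interval estimates will be obtained, and does not make this depend on the PFS result. If a share f of patients is too early, the expected ORR in each arm, and the difference between arms, is multiplied by (1 − f).

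**Working it through.** **Inputs from the documents.** Accrual of 120 patients over 18 months, 40 control and 80 experimental (Section 6.1). Cut at 80 events or 24 months (Section 6.4.1). Control median PFS 5–6 months (Section 3.3.6). Control ORR 33% (Section 6.1). Scan timing (Sections 4.5.5 and 4.2).

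**Assumptions.** FPI is the first randomised patient. Accrual is uniform unless stated. PFS is exponential with no dropout. The hazard ratio (HR) runs from 0.5 to 1.0, because the values in Table 11 are not visible. Confirmation comes at the scheduled Week 18 scan.

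**1. Follow-up needed.** 18 weeks + 6 days + 1 week = 19.9 weeks = 4.57 months. This allows the full scan window and the full delay to first dose.

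**2. The planned timeline.** The last patient has 24 − 18 = 6 months, or 26.1 weeks, against 19.9 needed. The latest randomisation that still allows Week 18 is month 24 − 4.57 = 19.4, after accrual ends. Patients affected: 0 of 120.

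**3. Reproducing the event timing.** With λ = ln 2 / median for control and HR × λ for the experimental arm, the event probability by month T (T ≥ 18) is

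D(T) = 1 − [exp(−λ(T − 18)) − exp(−λT)] / (18λ),

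and expected events are 40 × D(control) + 80 × D(experimental). At 24 months this gives 80 events (median 5.5, HR 0.5), 81 (median 6, HR 0.6) and 83 (median 5, HR 0.5). The pairing of 80 events with 24 months is therefore consistent with an HR of about 0.5–0.6. With a weaker effect, 80 events come earlier.

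**4. If 80 events set the cut.** Let T80 be the month when expected events reach 80. The share affected is f = [18 − (T80 − 4.57)] / 18, or zero if negative. Everyone has both scans once T80 ≥ 18 + 4.57 = 22.6 months.

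| HR | T80, months (control median 5 to 6) | Affected, of 120 |
|---|---|---|
| 1.0 | 18.7–20.0 | 26–17 |
| 0.8 | 19.8–21.4 | 19–8 |
| 0.7 | 20.5–22.3 | 14–2 |
| 0.6 | 21.5–23.5 | 7–0 |
| 0.5 | 22.9–25.3 | 0 |

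Example, HR 0.7 and median 5: [18 − (20.5 − 4.57)] / 18 = 11%, about 14 patients. These are counts at the expected timing. In a simulation with a 19-week requirement, chance variation in the date of the 80th event gave a mean of 0–2 patients at HR 0.5.

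**5. Against the interim projection.** Section 6.8.1 expects 50% event maturity at about 18 months, read here as 60 of 120. Uniform-accrual cases with about 60 events at 18 months (median 5 with HR 0.5; 5.5 with 0.6; 6 with 0.7) reach 80 events at 22.9, 22.5 and 22.3 months, with 0–2 patients affected. Back-loaded accrual (cumulative share proportional to time to the power 1.5) also gives about 60 events at 18 months with median 5 and HR 0.8, or median 6 and HR 1. It then puts 80 events at 21.2 and 21.5 months, with 13 and 11 affected.

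**6. If accrual slips and the 24-month cut is kept.** The share affected is (accrual length − 19.4) / accrual length: 3 patients at 20 months, 9 at 21, 14 at 22, 23 at 24.

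**7. Effect on ORR.** Take 33% against an assumed 53% (Table 12 values are not visible). Power is from the pooled two-proportion formula, 40 against 80, two-sided 5%.

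| f | ORR, control vs experimental | Difference | Power |
|---|---|---|---|
| 0 | 33.0% vs 53.0% | 20 points | 55% |
| 5% | 31.4% vs 50.4% | 19 points | 51% |
| 20% | 26.4% vs 42.4% | 16 points | 40% |

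**The case against.** The strongest reply is that the plan already leaves enough time. Six months separate the last planned randomisation from a 24-month cut, and every patient then reaches Week 18. This stands, and it makes the point conditional. On planned accrual, the problem arises only through the 80-event limb of an unresolved trigger, so it depends heavily on which limb governs.

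Second, ORR is tested formally only if PFS is significant. At 80 events that needs an observed HR of about exp(−1.96 / √(80 × 2/9)) = 0.63 or less, and at true HRs of 0.6 or below no more than 7 of 120 are affected. This limits the harm to the formal test. It does not protect the estimate, which is to be reported whatever PFS shows and is most diluted when the PFS effect is weak.

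Third, the counts lean high. The model sees progression at once, whereas the first scheduled scan is at Week 12. Dating progression to scheduled scans, with 20% of events assumed to be seen immediately, lowered simulated counts under a 19-week requirement from 4–13 to about 2–8 at HR 0.7 and from 1–7 to about 0–4 at HR 0.6. This is indicative only, since the cited medians may already include scan delay. Unscheduled scans, which Section 4.5.5 permits, would lower the counts further.

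A reader might also infer that the plan gives the interim a follow-up floor that it denies the final ORR, because "The first efficacy interim analysis will take place after either approximately 60 patients have had two scans". The documents do not support that. The two-scan count is one of two alternative triggers, the other being 25% PFS event maturity, and it covers only about half of the patients.

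**Conclusion.** The gap is real but conditional, and its severity is low. Final ORR has no follow-up floor. Patients too recent to have had both scans would stay in the denominator as non-responders if 80 events set the cut before about 22.6 months, or if accrual passed about 19.4 months with the 24-month cut kept. Under the assumptions above, the 80-event route affects at most about a fifth of patients (HR 1) and none at HR 0.5 or lower.

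A reader might infer that ORR and its difference are understated in the plan as it stands. They are not: at the planned 24-month cut the number affected is zero. If there is no true difference, none is lost. Because the expected share is the same in both arms, the effect is attenuation and does not manufacture a benefit.

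**What to change.** Add to Section 6.4.2 that final ORR is analysed in all randomised patients at the later of the primary PFS cutoff and about 20 weeks after the last randomisation. Stating in Section 6.4.1 which limb of the PFS trigger governs would remove most of the remaining uncertainty.

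Restricting the denominator to patients with enough follow-up is less attractive, because it departs from the all-randomised population in Sections 6 and 6.4. A 19-week limit would also be slightly too short, since the Week 18 scan can fall at 19.9 weeks.

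The cost is SAP wording. Nothing changes on the planned timeline. With 18-month accrual, the ORR readout would move by at most about 4 months in the cases above (22.6 − 18.7 = 3.9). With accrual of 22 months and the 24-month cut kept, it would move by 22 + 4.6 − 24 = 2.6 months. PFS timing is unaffected, and ORR would still be read before the final OS analysis at about 40 months, so the testing order holds.
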